7.2.1.5. Transitioning off Study Prandial Insulin Therapy

Patients will take their last prandial dose of study insulin (LY900014 or insulin lispro) at Visit 18 with the MMTT if performed the same date as Visit 18 or the evening the day prior to Visit 18 if the MMTT is performed prior to Visit 18 or at early discontinuation.

No special instructions for transition to nonstudy prandial insulin are necessary for patients who were using basal bolus therapy prior to study entry. After completion of study treatment, these patients will restart the prandial insulin therapy used prior to study entry, or may transition to a rapid-acting insulin analog other than insulin lispro if the patient was treated with regular human insulin prestudy.

Patients who were using premixed insulins or premixed insulin analogs prior to study entry may choose to stay on basal bolus regimen at the discretion of the investigator. However, patients who were not using insulin lispro prior to entry should NOT use insulin lispro during the safety follow-up period.

7.3. Blinding

This is a double-blind study. The treatment groups, LY900014 and insulin lispro, will be administered immediately (0-2 minutes) prior to each meal in a double-blind manner. Investigators, patients, and study site personnel will be blinded to assigned dosing regimens throughout the study.

To preserve the blinding of the study, the Lilly study team will remain blinded throughout the study; only a minimum number of Lilly personnel will see the randomization table and treatment assignments before the study is complete.

Emergency unblinding for AEs may be performed through the IWRS, which may supplement or take the place of emergency codes generated by a computer drug-labeling system. This option may be used ONLY if the patient's well-being requires knowledge of the patient's treatment assignment. Unblinding events are recorded and reported by the IWRS.

If an investigator, site personnel performing assessments, or patient is unblinded, the patient must be discontinued from IP and should remain in the study.

In case of an emergency, the investigator has the sole responsibility for determining if unblinding of a patient's treatment assignment is warranted. Patient safety must always be the first consideration in making such a determination. If the investigator decides that unblinding is

warranted, the investigator should make every effort to contact the Lilly clinical research physician (CRP/CRS) prior to unblinding a patient's treatment assignment unless this could delay emergency treatment of the patient. If a patient's treatment assignment is unblinded, Lilly must be notified immediately.

7.4. Dosage Modification

See Section 7.2.1.

7.5. Preparation/Handling/Storage/Accountability

The investigator or his/her designee is responsible for confirming appropriate temperature conditions have been maintained during transit for all study treatment received and any discrepancies are reported and resolved before use of the study treatment.

Only patients enrolled in the study may receive IP and only authorized site staff may supply or administer study treatment. All study treatments should be stored in an environmentally controlled and monitored (manual or automated) area in accordance with the labeled storage conditions with access limited to the investigator and authorized site staff.

All insulin products must be stored at the investigative site under refrigerated conditions (between 2°C and 8°C) in a locked and secure place. Insulin must not be frozen.

In-use insulins should be maintained at room temperature, and refrigerated material should be warmed to near room temperature before injection. In-use insulin must not be used after 28 days.

The investigator is responsible for study treatment accountability, reconciliation, and record maintenance (such as receipt, reconciliation, and final disposition records).

7.6. Treatment Compliance

The investigator or designee will assess compliance of the patient at each visit, based on a review of the patient's glycemic control, adherence to the visit and treatment schedule. Patients who are deemed noncompliant will receive additional diabetes education and training, as required, and the importance of compliance with the protocol will be reinforced. Patients who, in the opinion of the investigator, are deemed consistently noncompliant may be discontinued from IP or from the study. No specific study data will be collected for analysis of treatment compliance.

7.7. Concomitant Therapy

Guidance on restrictions for concomitant therapies is provided in [Table ITSE.8](#).

Table ITSE.8. Concomitant Medications

Drug Class	Acute Use	Chronic Use	Safety Follow-up Period	Conditions for Use
Sulfonylurea, meglitinide, DPP-4 inhibitor, alpha-glucoside inhibitor	No	No	Yes	
Thiazolidinedione, glucagon like peptide-1 receptor agonist	No	No	No	
NPH insulin, insulin glargine U-300, insulin detemir, insulin degludec U-200	No	No	Yes	May be used in emergencies for up to 14 consecutive days
Regular human insulin	No	No	Yes	May be used in emergencies for up to 14 consecutive days
Premixed insulin or premixed insulin analog	No	No	Yes ^a	May be used in emergencies for up to 14 consecutive days
Insulin human inhalation powder (Afrezza®)	No	No	No	
Weight loss drugs (for example: prescription drugs such as liraglutide, lorcaserin, orlistat, phentermine, phentermine/topiramate, naltrexone/bupropion; or over-the-counter weight loss medications)	No	No	Yes	
Systemic glucocorticosteroid (including IV, intramuscular, SC, or oral) but excluding non-systemic glucocorticosteroid (including topical, inhaled, intraocular, intra-articular, or intranasal preparations)	Yes	No	No	During the lead-in period, allow 1-time use for ≤14 consecutive days. During all other study periods, allow 1-time use a total of ≤21 consecutive days.

Abbreviations: DPP-4 = dipeptidyl peptidase-4; IV = intravenous; NPH = neutral protamine Hagedorn; SC = subcutaneous.

^a Patients who were using premixed insulins prior to study entry may choose to stay on basal bolus regimen. However, patients who were not on lispro product prior to entry should NOT use lispro product during the follow-up period

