6.2. Exclusion Criteria

Patients will be excluded from study enrollment if they meet any of the following criteria at screening:

Medical Conditions

- [14] Have any other condition (including known drug or alcohol abuse, psychiatric disorder including eating disorder) that precludes the patient from following and completing the protocol
- [15] Have been diagnosed, at any time, with T1D or Latent Autoimmune Diabetes in Adults
- [16] Have hypoglycemia unawareness as judged by the investigator
- [17] Have had any episode of severe hypoglycemia (defined as requiring assistance due to neurologically disabling hypoglycemia) within the 6 months prior to screening
- [18] Have had 1 or more episodes of diabetic ketoacidosis or hyperglycemic hyperosmolar state within the 6 months prior to screening
- [19] Have a known diagnosis of secondary diabetes (for example, diabetes caused by hemochromatosis, acromegaly, chronic pancreatitis, or pancreatectomy)
- [20] Excessive insulin resistance defined as having received a total daily dose of insulin >2.0 U/kg at the time of screening
- [21] Have a history of or are being evaluated for bariatric surgery including Roux-en-Y gastric bypass surgery, gastric banding, and/or gastric sleeve
- [22] Have clinically significant cardiovascular disease, within the last 6 months prior to screening, defined as stroke, decompensated heart failure New York Heart Association class III or IV ([Appendix 6](#)), myocardial infarction, unstable angina pectoris or coronary arterial bypass graft
- [23] Renal:
 - a) History of renal transplantation
 - b) Currently receiving renal dialysis
 - c) Serum creatinine >2.0 mg/dL ($177 \mu\text{mol/L}$) at screening
- [24] Hepatic: Have obvious clinical signs or symptoms of liver disease (for example, acute or chronic hepatitis or cirrhosis), or elevated liver enzyme measurements as indicated below at screening:
 - a) Total bilirubin level (TBL) $\geq 2X$ the upper limit of normal (ULN [with the exception of Gilbert's syndrome]) as defined by the central laboratory,
Or
 - b) Alanine aminotransferase (ALT) $\geq 3X$ ULN as defined by the central laboratory,
Or

- c) Aspartate aminotransferase (AST) $\geq 3X$ ULN as defined by the central laboratory

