- [25] Malignancy: Have active or untreated malignancy, have been in remission from clinically significant malignancy (other than basal cell or squamous cell skin cancer) for less than 5 years, or are at an increased risk for developing cancer or a recurrence of cancer in the opinion of the investigator
- [26] Have any hypersensitivity or allergy to any of the insulins or excipients used in this trial
- [27] Have hypersensitivity or allergy to the ingredients in the standardized test meal (for example, nut allergy)
- [28] Hematologic: Have had a blood transfusion or severe blood loss within 90 days prior to screening or have known hemoglobinopathy, hemolytic anemia, or any other traits of hemoglobin abnormalities known to interfere with measurement of HbA1c
- [29] Have presence of clinically significant gastrointestinal disease (for example, clinically active gastroparesis associated with wide glucose fluctuations) in the investigator's opinion

Prior/Concomitant Therapy

- [30] Have used thiazolidinediones, glucagon-like peptide 1 (GLP-1) receptor agonist, or pramlintide within 90 days prior to screening
- [31] Have used insulin human inhalation powder (Afrezza[®]) within 90 days prior to screening
- [32] Are currently taking traditional medicine (herbal medicine or patent medicine) with known/specified content of anti-hyperglycemic effects within 90 days prior to screening.
- [33] Have used CSII for more than 14 days within 90 days prior to screening
- [34] Glucocorticoid therapy: receiving chronic (lasting longer than 14 consecutive days) systemic glucocorticoid therapy (including IV, intramuscular, SC, or oral, but excluding topical, intraocular, intranasal, intra-articular and inhaled preparations) or have received such therapy within 8 weeks immediately prior to screening with the exception of replacement therapy for adrenal insufficiency
- [35] Have used any weight loss drugs (for example: prescription drugs such as liraglutide, lorcaserin, orlistat, phentermine, phentermine/topiramate, naltrexone/bupropion; over-the-counter weight loss medications; traditional/herbal medicine with known weight loss effects) within 90 days prior to screening

Prior/Concurrent Clinical Trial Experience

- [36] Are currently enrolled in any other clinical trial involving an IP or any other type of medical research judged not to be scientifically or medically compatible with this study

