8.1. Discontinuation from Study Treatment

In the event that a patient is discontinued from the study treatment, the investigator should encourage the patient to remain in the study for continued safety monitoring.

Lilly recognizes the importance of complete data collection. This study includes elements to minimize missing data. Randomized patients who are discontinued from IP before study completion are encouraged to remain in the study for continued monitoring. For patients who remain in the study after early discontinuation of IP, both efficacy (except MMTT) and safety data will be collected at scheduled visits. MMTT assessment will NOT be performed for these patients. The difference between stopping IP and discontinuing the study will be explained to patients as part of the informed consent, and patients will be encouraged to continue in the study even if they stop study drug. In addition, study site investigators will be trained on the importance of complete data collection, with additional re-education of sites and patients as necessary.

8.1.1. *Permanent Discontinuation from Study Treatment*

Patients will be discontinued from the IP in the following circumstances:

- The investigator may decide that the patient should stop IP. If this decision is made because of an AE, SAE, or a clinically significant laboratory value, the study drug is discontinued for that patient and appropriate measures are to be taken. Lilly or its designee is to be alerted.
- The patient requests to discontinue IP.
- If the patient becomes pregnant.
- If an investigator, study site personnel performing assessments, or patient is unblinded, the patient must discontinue IP.
- If the patient, for any reason, requires treatment with another therapeutic regimen or therapeutic agent that has been demonstrated to be effective for treatment of the study indication. Discontinuation from IP should occur prior to introduction of the new agent.
- Use of prohibited concomitant medication (see [Table ITSE.8](#)).
- If the patient has not taken IP for more than 14 consecutive days.
- **Discontinuation due to a hepatic event or liver test abnormality.** Patients who are discontinued from investigational product due to a hepatic event or liver test abnormality should have additional hepatic safety data collected via CRF.

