### 7.6. Sensitivity Analysis for Efficacy

The impact of COVID-19 on the efficacy of IP on the patients may come from different aspects such as prolonged treatment interruptions due to COVID-19 illness or control measures, study or treatment discontinuations due to COVID-19 illness or control measures, death due to COVID-19 and the usage of protocol prohibited medications to treat COVID-19. CCI

A sensitivity analysis will be conducted on the randomized patients without essential impact of COVID-19, i.e., the randomized patients who can't be classified into the above two groups. The MMRM and ANCOVA models as described in Section 6.11.1 and Section 6.11.3 respectively will be repeated as the models for the sensitivity analysis. If the conclusion differs from that of all randomized patients, the data and analysis will be further investigated.

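### Exclusion criterion [34] admits patients on adrenal-replacement glucocorticoids whom Table ITSE.8 and Section 8.1.1 would then stop, and the table's glucocorticosteroid row disagrees with itself on safety follow-up

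*Protocol*

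**What the plan says.** Three places in the protocol bear on systemic glucocorticoids.

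- **Section 6.2, criterion [34].** It excludes a patient who is "receiving chronic (lasting longer than 14 consecutive days) systemic glucocorticoid therapy" or who would "have received such therapy within 8 weeks immediately prior to screening", "with the exception of replacement therapy for adrenal insufficiency". The section's lead sentence fixes when the criteria apply: "Patients will be excluded from study enrollment if they meet any of the following criteria at screening".
- **Section 7.7, Table ITSE.8.** The glucocorticosteroid row covers systemic use, including oral, and leaves out only non-systemic preparations. Its cells for acute use, chronic use and safety follow-up read, in that order: "topical, inhaled, intraocular, intra-articular, or intranasal preparations) Yes No No". The conditions column allows one course of at most 14 consecutive days in the lead-in and then says: "During all other study periods, allow 1-time use a total of ≤21 consecutive days". Replacement therapy is not mentioned, and neither acute nor chronic is defined.
- **Section 8.1.1.** The circumstances in which IP is permanently stopped include "Use of prohibited concomitant medication", with a cross-reference to Table ITSE.8.

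Protocol Section 10.3.3.1 and SAP Section 6.11.1 restrict the primary HbA1c analysis to data from before permanent IP discontinuation. Protocol Section 8.1 rules out a mixed-meal tolerance test (MMTT) for patients who stay in the study after stopping IP.

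**The concern.** An exemption at entry has practical meaning only if the on-study rules also honour it. Replacement therapy for adrenal insufficiency is continuous, so a patient who enters under the exemption will go on taking a systemic glucocorticoid throughout. The table has no category that lets that patient continue, and Section 8.1.1 attaches permanent IP discontinuation to prohibited use. A site that follows the text exactly must stop a patient whom the protocol chose not to exclude. A site that assumes the exemption carries over will keep the patient.

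The row also gives two answers for the safety follow-up period. One site could record a steroid course there as a deviation while another treats it as permitted.

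For a randomized patient, the reading chosen could decide whether later HbA1c values enter the primary analysis and whether the Week 26 MMTT is done at all. SAP Section 6.11.4 plans no missing-data sensitivity analysis that would look at such losses.

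**Working it through.** This is mainly a comparison of texts. The documents state no figure for steroid use that could be reproduced.

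**1. Replacement therapy against the table's limits.** The inputs are the period lengths in Protocol Section 5.1 and the day limits in Table ITSE.8. I assume that replacement therapy is taken continuously.

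| Period | Length | Table limit | Continuous use within limit? |
|---|---|---|---|
| Lead-in | 8 × 7 = 56 days | 14 days | No |
| Treatment | 26 × 7 = 182 days | 21 days | No |
| Safety follow-up | 4 × 7 = 28 days | cell: none; conditions text: 21 days | No, on either reading |

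The patient passes criterion [34] and then breaks the table's rule in every period. The first breach is on day 15 of the lead-in, before randomization. Protocol Section 7.2 counts lead-in insulin lispro as IP, so Section 8.1.1 can be read as applying from then on.

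**2. Course lengths under each rule.** I compared courses of 1 to 35 days, taking more than 14 days as chronic.

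| Period | Allowed by conditions text | Allowed there but chronic by the [34] definition | Safety follow-up cell |
|---|---|---|---|
| Lead-in | 1–14 days | none | n/a |
| Treatment | 1–21 days | 15–21 days | n/a |
| Safety follow-up | 1–21 days | 15–21 days | No |

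The lead-in shows no clash between the two limits. In follow-up the cell and the conditions text disagree for every length from 1 to 21 days. On treatment, the 15–21 day overlap appears only if the screening definition is carried into the table.

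**3. Effect on power.** The plan's figure comes first (Protocol Section 10.1: margin 0.4, SD 1.1, 320 and 160 completers, 2-sided 95% interval):

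- SE = 1.1 × √(1/320 + 1/160) = 0.1065
- 0.4 / 0.1065 = 3.756, and 3.756 − 1.960 = 1.796
- Φ(1.796) = 0.964, which agrees with the stated 96%.

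For scale, assume 0 to 2 replacement patients. This is my assumption, since the documents give no number. In the worst case both are lost from the smaller arm: SE = 1.1 × √(1/320 + 1/158) = 0.1070, 0.4 / 0.1070 − 1.960 = 1.780 (unrounded SE), and power is 0.962. A patient stopped in the lead-in is never randomized and costs no completers.

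**The case against.** **The 15–21 day course.** A reader might infer that such a course is both forbidden and allowed. The documents do not support that. Criterion [34] is applied at screening, and its 14-day parenthesis defines a term inside that criterion. Table ITSE.8 neither cites it nor borrows its threshold, and states its own 21-day limit. In the three non-study insulin rows the conditions column also qualifies the No entries. This objection largely stands, and the likeliest reading is that the table's limit governs on treatment. It does not remove all doubt. In the insulin rows acute and chronic use are both No, so the condition can only be an exception. In the glucocorticosteroid row acute use is Yes, so the condition may simply cap that Yes and leave chronic use barred, with chronic undefined.

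**Replacement patients may not be enrolled.** Inclusion criterion [12] asks the investigator to judge the patient healthy apart from type 2 diabetes, and a breach detected in the lead-in occurs before there are any post-randomization data. Both points stand and keep the numbers small. Criterion [12] is a judgement, though, and the sponsor wrote an explicit exemption for these patients, so the texts still conflict.

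**The follow-up conflict does no statistical harm.** This stands. Study insulins end at Week 26, so for completers the HbA1c and MMTT are already collected. For patients who stopped IP early, the follow-up visit adds nothing to the on-IP Week 26 analysis.

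**COVID-19 analysis.** SAP Section 7.6 lists "the usage of protocol prohibited medications to treat COVID-19" as one way efficacy may be affected, and a reader might infer that this row decides how patients are grouped there. The text defining the groups is redacted, so that cannot be established.

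**Conclusion.** Two conflicts stand on the text. First, criterion [34] exempts adrenal replacement, while the Table ITSE.8 row and Section 8.1.1, taken literally, require stopping the same patient. Second, within that row the safety follow-up cell and the conditions text disagree; this affects deviation handling and conduct in follow-up, not the on-IP efficacy data. The undefined meaning of chronic is a lesser ambiguity.

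The size is small. With no rate in the documents, I do not estimate how many steroid courses would be affected. Under the assumption of 0 to 2 replacement patients, power stays between 0.962 and 0.964. Assignment is double-blind, and nothing in the documents suggests that the two arms would be affected differently, so I do not claim bias in the treatment comparison. Correction is worthwhile because the consequence for an individual patient is permanent loss of IP under a rule that contradicts the entry criteria. A randomized patient stopped this way would have no later MMTT, and HbA1c outside the SAP's 14-day on-IP window would leave the primary analysis. The conclusion rests on replacement therapy being continuous and on Section 8.1.1 being applied as written.

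**What to change.** Reconcile criterion [34], the glucocorticosteroid row of Table ITSE.8 and Section 8.1.1 on three points:

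1. Treat replacement therapy for adrenal insufficiency the same way in all three places.
2. Make the safety follow-up cell and the conditions text agree.
3. State in the table what chronic use means, so that a site need not look to a screening criterion for it.

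Which exception, limit and follow-up rule apply is a decision for the sponsor's medical team. No SAP change is requested on this point.

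The cost is a minor change to protocol text, which goes to the ethics review boards under Appendix 3.1.2, and a clarification to sites. A few courses already recorded under a different reading may have to be reclassified.

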7.7.1. Management of Oral Antihyperglycemic Medications

During the study lead-in and treatment periods, patients may continue the use of up to **2 of the following OAMs: metformin, SGLT2 inhibitor in accordance with local regulations**. Please also refer to Exclusion Criterion [30] for criteria regarding thiazolidinediones, GLP-1 receptor agonists, and pramlintide (Section 6.2). Other prestudy OAMs including sulfonylurea,

meglitinide, DPP-4 inhibitor, and alpha-glucosidase inhibitor agents will be discontinued at the beginning of the lead-in period (Visit 2).

Oral antihyperglycemic medication dosing is to remain stable during study lead-in and treatment, except with the development of contraindications or for safety reasons. During study lead-in and treatment, all glycemic management is to be conducted by adjustment of basal and prandial insulin doses. In emergency situations, it may be necessary for patients to change their dose of OAM and/or be treated with a nonstudy insulin. This will be allowed for up to 14 consecutive days (Section 8.1.2).

